17.0 Pathology Considerations/Tissue Biospecimens NA.....	58
18.0 Records and Data Collection Procedures.....	58
19.0 Budget.....	59
20.0 References.....	60
Appendix I ECOG Performance Status.....	62

Schema

*Sample collection under IRB#14-009163, IRB#919-04, or IRB#521-93

**Dosing and regimen as per section 7

***Patients who discontinue treatment before completing 6 cycles for any reason will go off study (No SFU/CFU).

[†]Cycle 1 = 21. Cycles 2 – 6 = 28 days

Generic name: Lenalidomide	Generic name: Pomalidomide	Generic name: Dexamethasone
Brand name(s): Revlimid	Brand name(s): Pomalyst	Brand name(s):
Mayo Abbreviation:	Mayo Abbreviation:	Mayo Abbreviation:
Availability: Commercial	Availability: Commercial	Availability: Commercial

1.0 Background

Multiple myeloma (MM) is a clonal plasma cell malignancy that tends to affect the older patient with a median age at onset of 65-70 years and a slight male predominance. The American Cancer Society estimates that about 30,330 new cases of MM will be diagnosed in 2016, and about 12,650 patients will die of the disease.(1) Patients with MM can experience bone pain, bone fractures, fatigue, anemia, infections, hypercalcemia and kidney problems.(2) Treatment options are based on the patient's disease status. Standard treatments for MM include combination chemotherapy regimens containing proteasome inhibitors (PIs) such as bortezomib and carfilzomib, and/or immunomodulatory drugs (IMiDs), such as lenalidomide and pomalidomide, in combination with corticosteroids.(3) Alkylating agents such as melphalan and cyclophosphamide are also active in MM.(3) Patients under the age of 75, who are free from significant comorbidities, are often treated with myeloablative chemotherapy and/or radiation, followed by autologous stem cell transplantation (ASCT).(3) These treatments have improved outcomes of patients with MM in recent years, both in the relapsed setting as well as at diagnosis.(4)

However, despite considerable improvements in therapy, MM relapses remain inevitable and mostly incurable making it uniformly fatal with a median overall survival of around 8 years.(5) This is because MM cells actively evolve to develop resistance mechanisms against the cytotoxic effects of therapies that they are exposed to eventually leading to the exhaustion of all therapeutic options. In general, MM patients will receive an average of 4 to 8 different regimens during their lifespan utilizing agents such as proteasome inhibitors (e.g., bortezomib, ixazomib and carfilzomib), anti-CD38 monoclonal antibodies (e.g., daratumumab and isatuximab), immune modulatory agents (e.g., lenalidomide and pomalidomide), etc.(5) Currently, these aforementioned highly effective drug combinations used are beset with a various degrees of toxicity that precludes long-term therapy and also can affect the quality of life metrics. Furthermore, we are currently unable to reliably predict in advance whether a particular therapy would be effective or not until after administering it to a patient. This exposes patients to potential side effects from treatments that may not be beneficial in their case. In order to continue the pursuit of improving the overall survival and quality of life of MM patients, it is critical that we identify predictive biomarkers of response to therapies that will produce deep and durable remissions while at the same time alert patients and physicians of therapies that are unlikely to be successful.

1.1 Immunomodulators (IMiDs) as effective therapies in MM

The immunomodulatory drugs or IMiDs include thalidomide, lenalidomide and pomalidomide. These drugs have contributed to improvement in the overall survival of patients with MM. These drugs work through a variety of mechanisms due to its pleiotropic effects on multiple myeloma cells and the remainder of the cells associated with the immune system. IMiDs are widely used as induction therapy for both transplant eligible and ineligible patients, in the post-transplant maintenance setting, and for relapsed/refractory disease. As such, they remain the backbone of therapy for both newly diagnosed and relapsed disease.

Lenalidomide: The initial phase I study determined the maximal tolerated dose to be 25 mg (6). In terms of response rates, in the patients previously treated, studies revealed overall response rates of 48–61% and 46–57% in which most patients were previously treated with thalidomide(7-9). In the newly diagnosed setting, lenalidomide with dexamethasone was found to have an overall response rates of 68–91%.(10, 11) As a result, this regimen has replaced the use of thalidomide/dexamethasone as one of the most commonly used induction regimens in the United States. However, the administration of lenalidomide with dexamethasone changed when a study

comparing “high-dose” dexamethasone (40 mg days 1–4, 9–12, 17–20 of a 28-day cycle) to “low-dose” dexamethasone (40 mg days 1, 8, 15, 22 of a 28-day cycle) in combination with lenalidomide revealed a better one-year overall survival rate with an improved side effect profile for the low-dose weekly dexamethasone(11). This weekly dosing of dexamethasone is now routinely used in almost all myeloma regimens. More recently, the triplet combination of lenalidomide, bortezomib, and dexamethasone(12) has become a standard of care of newly diagnosed patients as it was found to provide a better progression free survival and overall survival compared to just lenalidomide and dexamethasone. In the post-transplant maintenance setting, lenalidomide is also widely used. Several randomized phase III studies have been performed, all of which have demonstrated significant PFS benefit with lenalidomide (13-15) including the CALGB 100104 study which revealed a significant OS benefit (13). A recent meta-analysis of the three studies assessing maintenance lenalidomide post-transplant confirmed an OS benefit(16).

Pomalidomide: This third generation IMiD was approved for the treatment of relapsed/refractory myeloma in 2013 for patients who had received at least two prior regimens including lenalidomide and bortezomib. This agent has only been evaluated in the previously treated setting. In one phase II study, the combination of pomalidomide and dexamethasone where the pomalidomide was dosed at 2 mg daily had a 63% overall response rate including 40% ORR in lenalidomide-refractory patients and 37% ORR in thalidomide-refractory patients(17). In another study which included only lenalidomide-refractory patients, the overall response rate was 47%(18). An alternative dosing strategy of 4 mg daily for 21 out of 28 days was also explored and the ORR was 35–42% (19, 20).

1.2 Rationale for the current trial

Current treatment regimens in both the upfront and relapsed settings have trended towards utilizing combination therapies that include a combination of an IMiD with proteasome inhibitors and/or monoclonal antibodies(21, 22). This is largely due to the results of several phase III clinical trials demonstrating the overall benefit of three-drug regimens (triplets) containing IMiDs and proteasome inhibitors or IMiDs and monoclonal antibodies over two-drug regimens (doublets) containing IMiDs alone with dexamethasone in terms of their depth and duration of hematological response. However, some patients within these clinical trials as well as in real-world clinical practice may derive equal depth and duration of therapeutic response to two-drug regimens (doublets) containing IMiDs alone with dexamethasone compared to triplets. At this time, our gap in knowledge prevents us from *apriori* identifying those patients who can be spared the physical and financial toxicity of adding the additional third or fourth agent such as proteasome inhibitors and/or monoclonal antibodies to an IMiD and dexamethasone. Being able to develop and validate biomarkers capable of filling this fundamental gap of knowledge could have practical implications to the clinical care of patients with MM. **As such, this study will provide the possibility of obtaining biospecimens from untreated smoldering MM and MM patients as well as previously treated MM patients pre- and post-treatment with one cycle of therapy containing only an IMiD and dexamethasone.**

Furthermore, it has been long hypothesized that there may be a differential response to IMiDs for patients belonging to African American (AA) race. Small studies have suggested that AA patients may have a better response to IMiDs than whites but receive a lesser access to these agents. This has led to the need for a more definitive testing to develop an efficacy profile as well as biomarker identification which may help predict the differences in response among AA and white patients with MM.

2.0 Goals

2.1 Primary Goal

To determine response rates (>=PR) of prospectively treated MM patients with one cycle of therapy containing a combination of an immunomodulator and dexamethasone.

2.2 Secondary Goals

1. To identify biomarkers that predict response rates of untreated smoldering MM and MM patients to a combination of an immunomodulator and dexamethasone.
2. To compare response rates of MM among AA and white patients to a combination of an immunomodulator and dexamethasone.
3. To establish correlation of biomarkers in treated MM patients with the combination of an immunomodulator and dexamethasone to the depth of hematological response observed in new or previously treated patients.

3.0 Registration Patient Eligibility

3.1 Registration - Inclusion Criteria

3.11 Age \geq 18 years

3.12 **Cohort A:** Patient must have untreated smoldering multiple myeloma which is defined by the presence of 10% or more but less than 60% clonal plasma cells in the bone marrow and the absence of any of the following myeloma related symptoms or laboratory and radiographic abnormalities: anemia, hypercalcemia, renal insufficiency, hypercalcemia, serum free light chain ratio of greater than 100 or more than one focal marrow multiple myeloma lesion on MRI imaging.

Cohort B: Patient must have newly diagnosed myeloma requiring treatment and no prior therapies

Cohort C: Patient must have relapsed or refractory multiple myeloma with at least one prior therapy for their multiple myeloma but not refractory to all IMiDs

Cohort D: Patient must have relapsed or refractory multiple myeloma with Lenalidomide as part of a maintenance regimen as their most recent therapy

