5.0 Grouping Factor

5.1 Multiple Myeloma Cohort: Cohort A (Smoldering MM), Cohort B (Newly Diagnosed MM), Cohort C (Relapsed/Refractory MM) and Cohort D (Relapsed on Len maintenance).

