7.0 Protocol Treatment

7.1 Treatment Schedule

Cohort A and B Cycle 1

Treatment medication table. Patient may receive Lenalidomide OR Lenalidomide + Dexamethasone.

Agent	Dose Level	Route	Day	Re Rx
Lenalidomide	25 mg*	Oral	Cycle 1: Day 1-14	Cycle 1: 21 days
Dexamethasone	40 mg**	Oral	Cycle 1: Day 1 ,8, ,15	Cycle 1: 21 days

Cycle 1 length = 21 days

* Starting dose will be determined as per the creatine clearance below (see 7.12)

**The dose of dexamethasone used can be determined by the treating physician and omitted if needed.

Cohort C and D Cycle 1

Treatment medication table. Patient may receive Lenalidomide + Dexamethasone OR Pomalidomide + Dexamethasone.

Agent	Dose Level	Route	Day	ReRx
Lenalidomide	25 mg*	Oral	Cycle 1: Day 1-14	Cycle 1: 21 days
Pomalidomide	4 mg	Oral	Cycle 1: Day 1-21	Cycle 1: 21 days
Dexamethasone	40 mg**	Oral	Cycle 1: Day 1 ,8, ,15	Cycle 1: 21 days

Cycle 1 length = 21 days

* Starting dose will be determined as per the creatinine clearance below (see 7.12)

** The dose of dexamethasone used can be determined by the treating physician and omitted if needed.

Cohort A and B Cycles 2-6

Treatment Medication Table. Patient may receive Lenalidomide based regimens.

Agent	Dose Level	Route	Day	Re Rx
Lenalidomide	25 mg*	Oral	Cycle 2-6: Day 1-21	Cycles 2-6: 28 days
Dexamethasone	40 mg**	Oral	Cycle 2-6: Day 1 ,8, ,15, 22	Cycles 2-6: 28 days

Note: Standard of care agents can be added for cycles 2-6 as long as the regimen contains lenalidomide

Cycles 2-6 length = 28 days

* Any dose-adjustments will be determined as per the creatine clearance below (see 7.12).

** The dose of dexamethasone used can be determined by the treating physician and omitted if needed.

Cohort C and D Cycles 2-6

Treatment medication table. Patient may receive Lenalidomide based regimen OR Pomalidomide based regimen.

Agent	Dose Level	Route	Day	ReRx
Lenalidomide	25 mg*	Oral	Cycles 2-6: Day 1-21	Cycles 2-6: 28 days
Pomalidomide	4 mg	Oral	Cycles 2-6: Day 1-21	Cycles 2-6: 28 days
Dexamethasone	40 mg**	Oral	Cycle 2-6: Day 1,8,15,22	Cycles 2-6: 28 days

Note: Standard of care agents can be added for cycles 2-6 as long as the regimen contains lenalidomide or pomalidomide

Cycles 2-6 length = 28 days

* Any dose-adjustments will be determined as per the creatinine clearance below (see 7.12).

** The dose of dexamethasone used can be determined by the treating physician and omitted if needed.

7.12

Creatinine Clearance (CrCl)	Lenalidomide Dose

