12.0 Descriptive Factors

- 12.1 Prior treatment: 0 vs 1 vs 2 vs 3+
- 12.2 Parameters followed for hematologic response: serum monoclonal protein ≥ 0.5 g/dL and urine monoclonal protein ≥ 200 mg/24 hours vs. serum monoclonal protein ≥ 0.5 g/dL only vs. urine monoclonal protein ≥ 200 mg/24 hours only vs. serum immunoglobulin free light chain ≥ 10 mg/dL vs. bone marrow plasma cells $\geq 30\%$ vs. measurable bone or extramedullary disease on imaging. Distinguish between SPEP measurements versus quantitative IgA measurements versus quantitative IgD measurements for serum monoclonal protein.
- 12.3 mSMART FISH risk level: high risk vs low risk vs unknown.

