16.32 Secondary Outcome Analyses

16.321 Biomarkers and RR will be analyzed using logistic regressions to identify predictive biomarkers.

16.322 RR among African American (AA) patients and white MM patients will be evaluated after one cycle of treatment. Chi-Square (or Fischer Exact) test and 95% confidence intervals will be estimated to compared AA and white patients descriptively.

16.323 Correlation between the depth of hematological responses and biomarkers will be estimated. Logistic regressions and chi square (or Fischer exact) testing will be utilized.

16.33 Data & Safety Monitoring:

The principal investigator(s) and the study statistician will review the study at least twice a year to identify accrual, adverse event, and any endpoint problems that might be developing. The Mayo Clinic Cancer Center (MCCC) Data Safety Monitoring Board (DSMB) is responsible for reviewing accrual and safety data for this trial at least twice a year, based on reports provided by the MCCC Statistical Office.

Adverse Event Stopping Rules: (Each cohort will be analyzed separately) The stopping rules specified below are based on the knowledge available at study development. We note that the Adverse Event Stopping Rule may be adjusted in the event of either (1) the study re-opening to accrual or (2) at any time during the conduct of the trial and in consideration of newly acquired information regarding the adverse event profile of the treatment(s) under investigation. The study team may choose to suspend accrual because of unexpected adverse event profiles that have not crossed the specified rule below.

Accrual will be temporarily suspended to this study if at any time we observe events considered at least possibly related to study treatment (i.e. an adverse

event with attribute specified as “possible”, “probable”, or “definite”) that satisfy either of the following:

- If 3 or more out of the first 10 treated patients experience grade 4+ non-hematological toxicities
- If after the first 10 patients have been treated, 30% of patients experience grade 4+ non-hematologic toxicities

We note that we will review grade 5 adverse events deemed “unrelated” or “unlikely to be related”, to verify their attribution and to monitor the emergence of a previously unrecognized treatment-related adverse event.

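### In Cohorts C and D neither IMiD-refractory status nor the IMiD received is an analysis factor, so a marker that only tracks refractoriness can appear associated with response

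*Combined protocol and SAP*

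**What the plan says.** **Who enters.** For Cohort C, Section 3.12 asks for a "Patient must have relapsed or refractory multiple myeloma with at least one prior therapy for their multiple myeloma but not refractory to all IMiDs". For Cohort D it states: "Patient must have relapsed or refractory multiple myeloma with Lenalidomide as part of a maintenance regimen as their most recent therapy". The Cohort D rule has no limit on refractoriness, and the documents nowhere define refractory.

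**What they receive.** For both cohorts in cycle 1, Section 7.1 says "Patient may receive Lenalidomide + Dexamethasone OR Pomalidomide + Dexamethasone". Nothing links the choice to earlier IMiD exposure or resistance.

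**What is recorded as a factor.** Section 5.1 has one grouping factor, the cohort. Section 12 has three descriptive factors: the number of earlier treatments ("Prior treatment: 0 vs 1 vs 2 vs 3" or more), the parameter followed for response, and FISH risk level.

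**What is analysed.** Sections 16.2 and 16.31 estimate the response rate after one cycle by biomarker category, separately in each cohort. Section 16.321 adds: "Biomarkers and RR will be analyzed using logistic regressions to identify predictive biomarkers". Section 16.323 relates biomarkers to depth of response by logistic regression and chi-square or exact tests. No covariate is named in either.

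**What the background reports.** Section 1.1 cites a phase II study of pomalidomide-dexamethasone with a "63% overall response rate including 40% ORR in lenalidomide-refractory patients".

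**The concern.** Section 1.2 gives the purpose: to know in advance which patients do well enough on an IMiD and dexamethasone to be spared further agents. A marker helps only if it says something the treatment history does not already say.

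Cohort C can hold IMiD-naive patients, exposed but not refractory patients, and patients refractory to some but not all IMiDs. Cohort D holds lenalidomide-exposed patients who may or may not be refractory. In both, some may receive lenalidomide and others pomalidomide. If refractoriness lowers response and a marker is more common in refractory disease, the unadjusted comparison credits the marker with the effect of the history. Section 16.2 intends these results to suggest further studies, so a confounded lead would be carried forward. The Cohort C and D response rates would also be hard to compare with other series if the mix behind them is not reported.

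**Working it through.** **1. The plan's own figure.** Section 16.22 gives 30 evaluable patients in each of A and B and 60 in each of C and D, plus 2 and 3 extra: 2 × (30 + 2) + 2 × (60 + 3) = 190, the stated maximum. There is no power or effect size to reproduce. The relevant size is 60 per cohort.

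**2. Response by refractoriness.** Section 1.1 gives 63% overall and 40% in lenalidomide-refractory patients. If a share f of that study was refractory, the rate in the others is (63 − 40f)/(1 − f). The documents do not give f.

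- f = 0.2: 68.8%
- f = 0.3: 72.9%
- f = 0.4: 78.3%
- f = 0.5: 86.0%

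Taking 63% itself as the non-refractory rate therefore understates the gap in that study.

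**3. Apparent marker effect.** Suppose half the cohort is refractory, response is 63% against 40%, and a marker with no effect of its own agrees with refractory status in a proportion a of patients.

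- Marker-positive rate: 40a + 63(1 − a)
- Marker-negative rate: 63a + 40(1 − a)
- Difference: 23(2a − 1) points

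For a = 0.7, 0.8 and 0.9 the difference is 9.2, 13.8 and 18.4 points. At a = 0.8 the rates are 44.6% and 58.4%.

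**4. How often this is flagged.** I simulated 40,000 cohorts of 60 per scenario. Response depended only on refractory status. I compared a crude 2×2 chi-square test, standing in for an unadjusted logistic regression, with a Mantel-Haenszel test stratified by refractory status. Both were two-sided at a nominal 5%. The Monte Carlo standard error is at most √(0.25/40,000) = 0.25 points.

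| Refractory share (assumed) | Response, not refractory vs refractory | Unadjusted flags at 70 / 80 / 90% agreement | Stratified flags |
|---|---|---|---|
| 50% | 63% vs 40% | 11.3 / 19.0 / 30.3% | 4.8 / 4.9 / 4.2% |
| 30% | 63% vs 40% | 9.8 / 15.8 / 25.1% | 5.1 / 5.0 / 4.3% |
| 30% | 72.9% vs 40% | 15.1 / 28.3 / 47.1% | 4.9 / 4.7 / 4.1% |
| 50% | 86% vs 40% | 31.4 / 60.8 / 85.5% | 4.9 / 4.8 / 4.0% |
| 50% | 40% vs 20% (lower rates, assumed) | 10.1 / 17.5 / 27.5% | 4.9 / 5.0 / 4.5% |

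At 50% agreement, where the marker is unrelated to refractoriness, the unadjusted rate is 5.0-5.4%. The excess therefore comes from the confounding.

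**5. Price in precision.** At an observed 50% response, the exact 95% interval is 37-63% for n = 60, 31-69% for n = 30 and 27-73% for n = 20.

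**The case against.** **Cohort already carries part of this history.** Cohorts are analysed separately, D isolates patients whose last therapy was lenalidomide maintenance, and C excludes those refractory to all IMiDs. This stands: it is wrong to say that nothing captures IMiD history, or that every cohort mixes naive, exposed and refractory patients. Cohort D cannot contain an IMiD-naive patient. The label in Section 5.1 even suggests that all of D relapsed while on lenalidomide, although Section 3.12 does not require it. But cohort does not separate refractory from non-refractory patients within C, nor lenalidomide from pomalidomide recipients within C or D.

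**The cited rates transfer poorly.** They come from one study of pomalidomide 2 mg, whereas Section 7.1 lists 4 mg, and they are not stated as one-cycle rates. Section 1.1 also reports 47% in a study of lenalidomide-refractory patients only. Using that figure across studies, with f from 0.2 to 0.4, the gap is 20-27 points instead of 29-38. This stands as a limit on size.

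**It is a pilot focused on estimation.** True, but confounding distorts estimates as much as tests, and Section 16.321 sets out to identify predictive markers.

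**The first secondary goal may cover untreated patients only.** It can be read so. The response rate by biomarker and Section 16.321 carry no cohort limit, however, and the third goal names previously treated patients.

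**Adjustment may remove the biology sought.** Refractoriness is how IMiD resistance shows itself clinically. If marker and status agree fully, a stratified analysis can never flag the marker. This is a good reason to show both results, and not to require that a marker add to treatment history before it is called predictive.

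**The data may exist anyway.** Section 4 requires a complete medical history and Section 18.5 relapse documents. That makes the remedy cheap, but supplies no definition, variable or planned adjustment.

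**Conclusion.** The point holds for Cohorts C and D and should be settled before the biomarker analysis is fixed. As written, the analyses in 16.31, 16.321 and 16.323 cannot distinguish a marker of response from a marker of refractoriness. With half the cohort refractory and 63% against 40% response, a marker with no effect of its own is flagged in about 11-30% of 60-patient cohorts at 70-90% agreement, against 4-5% when stratified. Larger gaps give more.

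This is a risk, not a demonstrated bias. The refractory share and the agreement are assumptions, and one-cycle gaps may be smaller. The documents give no response figure for an IMiD to which the patient is already refractory.

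A reader might infer that the Cohort C and D response rates describe no definable population. That goes too far: Section 3.12 defines both cohorts. What is missing is a planned report of the mix. Nor do the documents show that the history cannot be recovered; only its definition and use are unplanned.

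**What to change.** 1. Define IMiD-refractory in the protocol.
2. In Section 12, for Cohorts C and D, add status for each prior IMiD (not exposed; exposed, not refractory; refractory) and the IMiD received in cycle 1. Status to the IMiD given is not enough alone: a lenalidomide-refractory patient receiving pomalidomide for the first time would be coded as unexposed, which hides the contrast cited in Section 1.1.
3. In 16.31, report Cohort C and D response rates descriptively by these factors, with exact 95% intervals.
4. In 16.321 and 16.323, give each marker's association in these cohorts both unadjusted and adjusted for (or stratified by) refractory status and IMiD received, and interpret the two together.

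The cost is one or two CRF items, a few extra model terms and the wider stratum intervals shown above. With 60 patients the adjusted results will be imprecise and should be presented as such. Eligibility, accrual and treatment do not change.
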